The costs of treatment are calculated as the unit costs of a specific treatment, multiplied by the frequency with which that treatment is used. A distinction is made between the treatment use for a screen-detected tumour and the treatment use for a clinically diagnosed tumour outside or without a screening programme. We include over-treatment, i.e. treatment of tumours that would not have been clinically diagnosed if there were no screening programme. Direct and indirect short- and long-term treatment costs are incorporated. To account for stage shifting due to screening and its consequences on the treatment costs, specific treatment probabilities for each separate tumour stage are needed. Treatment use is further specified for the age groups.

Analyses by risk (stratification)

Multiple single nucleotide polymorphisms combined together are translated into a polygenic risk score to stratify women based on their polygenic risk. In this figure, a simplified analysis of using polygenic risk to inform screening strategies is demonstrated by dividing the population into three (low, median, and high) risk groups with varying risk and prevalence. In this example 10% of the population is classified as low risk, 80% is classified as average risk, and 10% as high risk. Compared to the average risk group, more frequent screening could be offered to the high risk group and less frequent screening could be offered to the low risk group. With more risk groups, or even a continuous risk distribution we can “optimize” the tailoring of screening strategies based on polygenic risk. This would lead to a re-distribution of the benefits and harms of routine screening compared to the current “one size fits all” mammography screening approach that is merely based on a woman’s age.

Preliminary modeling indicates that targeted screening based on (so far published) genetic risk profiles only, led to more benefits than untargeted screening for the same number of screens. A screening strategy with an earlier starting age (40y) for the 10% at highest risk and a later starting age (60y) for the 10% at lowest risk

led to substantial benefits in the high risk group (an increase in deaths averted of 19.8%), and translated into an increase in life-years gained of 3.6% (figure). For this proposal, we will however also include our density stratification, and extended model by ER/HER-status, being able to make more precise predictions across a broader spectrum of ages. The models can incorporate co-morbidity, if substantial high quality data can be gathered in the project. At age 40 years, women in the simulated model cohorts are assigned an initial breast density on the basis of the distribution of BI-RADS density categories for premenopausal women in the Breast Cancer Surveillance Consortium (BCSC) women. At age 50 years, women are assigned to the same breast density category or the next lower category so the prevalence of breast density categories matched the BCSC observed prevalence for postmenopausal women. Sensitivity and specificity of digital mammography are determined as a function of age, breast density, and screening interval. The current model incorporates modeling of molecular tumor subtypes and evaluates benefits under screening and adjuvant treatment regimens by molecular subtypes (Munoz et al).

Special attention will be given to the different recruitment strategies in the European countries involved, and possible future other recruitment strategies considered. Also, the substantial differences in health care systems and cultural differences across countries will be considered, possibly in different country-specific models and costing. For Israel, we will add a specific high risk group (and possibly different natural history model) for Ashkenazi Jews. Finally, sensitivity analyses will be performed, e.g., on expected risk levels, different cut-offs for screening strategies, sensitivity and specificity for subgroups (if limited data), participation rates, and opportunistic screening, treatment effect, cost and screening effect.

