Amongst the potential harms of risk-stratified screening are undue increases in general anxiety or distress related to cancer. The results from PROCAS1 and RIVIERA studies found little evidence for elevated distress, although distress was higher in women who received higher risk results (Evans et al 2016, Veron et al 2018). To assess if increased distress is a harm of risk-stratified screening, we will compare the levels of general anxiety and cancer-specific worry between women who receive risk-stratified screening and women who receive standard screening. It is generally found that cancer-specific worry measures are more sensitive to the effects of receiving risk information than more general measures of anxiety (Bond 2013; Nelson 2016). In contrast, there is better evidence that more general measures of anxiety are better linked to diagnoses of psychological disorders (Spiegelhalter, 1983). For this reason we will assess both indices of psychological distress. We will assess both variables using standardized measures: the STAI short form to assess general state anxiety (1992) and the Lerman cancer-worry scale (1991).

There is also evidence that both general anxiety and cancer-related worry peak shortly after receiving information on cancer risk (Bond 2013; Nelson 2016) and then gradually decline. For this reason, we will assess these variables over time across five countries, to examine whether there are short-term increases as well as any longer-term effects.

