7.3 Baseline visit (V0)

Women eligible for the study and having signed the informed consent form will perform a baseline visit. Women can be provided with the informed consent sheet and have a 2 weeks reflection time potential interval before trial accrual.

Upon signature of the informed consent, women can be immediately randomized either in standard screening arm or in risk-based arm.

During this visit, the investigator has to create the profile of the woman into the web-platform and to interview the woman for retrieving medical history and medical data.

Women have to answer the following questionnaires (via a touchpad, a phone or via their own profile on web-platform):

- Socio-demographic and economical status questionnaire
- Comprehension questionnaire
- State anxiety
- Quality of life (EQ-D)

After written informed consent has been obtained, the study site will obtain a unique patient number or unique patient identifier which will stay the same throughout the entire study covering all study periods (as described in section 12). At this time point the patient is enrolled into the study.

Women who have signed the informed consent and fulfill all eligibility criteria will be randomized directly online by the investigator, 1:1 to either standard-of-care screening or a risk-based screening strategy.

Women will be randomized for either arm immediately during the accrual visit through the use of the online real-time randomization module of the trial.

The results of the randomization will be immediately provided. See study scheme.

- Women randomized to the standard arm will immediately receive their personal "standard" screening schedule for the next 4 years. No other visit with the investigator is formally planned.
- Women randomized to the risk-based arm will be asked to provide a saliva sample. Their breast density will be evaluated. They will be scheduled for a second visit (physical or by telephone interview according to national/local regulations), during which they will be communicated their risk estimation and their personalized, risk-based, screening schedule/plan for the next 4 years. The saliva sample will be sent to the central lab for DNA extractions and genotyping.

7.4 Visit 1 or phone call (more and less 8 - 12 weeks after the randomization date - V0) only for women randomized in risk-based screening program

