Appendix 4: Participants' questionnaires

The following questionnaires will be used in this study:

- Socio-demographic and economical status questionnaire
- Comprehension questionnaire
- STAI short form (state anxiety)
- Quality of life (EQ-D)

TABLE 1 – SOCIO-PSYCHOLOGICAL QUESTIONNAIRES

VISITS	Baseline	Risk-based screening arm	Follow-up	
Visits n°	Visit (V0)	V1	NA	NA
Visit Dates	D0	V0 + 8-12 weeks	M12 +/- 6 months	M48 +/- 6 months
Type of visit	physical	physical or telephone call	On-line	On-line
QUESTIONNAIRE				
1. STAI short form (state anxiety)	X	X	X	X
2. Comprehension questionnaire	X	X		X
3. Information seeking-behavior questionnaire		X		X
4. Quality of life (EQ-5D)	X			X
5. Satisfaction			X	X
6. Socio-demographic and economical status questionnaire	X			X

STAI short form

A number of statements which people have used to describe how they feel are given below. Please read each statement and then circle the most appropriate number to the right of the statement to indicate how you feel right now, at this moment. There are no right or wrong answers. Do not spend too much time on any one statement but give the answer which seems to describe your present feelings best.

	Not at all	Somewhat	Moderately	Very much
1. I feel calm	1	2	3	4
2. I am tense	1	2	3	4
3. I feel upset	1	2	3	4
4. I am relaxed	1	2	3	4
5. I feel content	1	2	3	4
6. I am worried	1	2	3	4

Comprehension & Information seeking-behaviour questionnaire

Comprehension

Frequency : Baseline, +3/5m, +4y

Below are some questions about breast cancer screenings. Some sentences are true, others are false. Take your time, and for each question, please circle the answer that you think is correct.

Circle only one answer

TRUE

FALSE

BREAST CANCER

1. Breast cancer is the most common cancer for women in occidental country
2. We can always cure breast cancer

BREAST CANCER SCREENINGS

3. Screening makes it possible to detect cancer as early as possible before it gives symptoms
4. The sooner you detect breast cancer, the easier it is to heal it
5. Mammography screening consists of making a breast x-ray on a regular basis
6. Stratified screening relies on a saliva sample to analyse DNA
7. Calculating individual risk include information on age, family history of cancer, biopsy history, breast density

BREAST CANCER SCREENINGS' BENEFITS AND RISKS

1. Mammography can be painful.
2. Breast cancer screening reduces breast cancer mortality by an average of 20%. In other words, it avoids 1 out of 5 deaths.

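### The cancer-worry scale promised for a between-arm comparison is in no schedule, and the only early anxiety measurement after baseline is taken in the risk-based arm alone

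*Protocol*

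**What the plan says.** **The aim.** In Section 1.1.24 (psycho-social impact of both screening methods) the sponsor writes: "we will compare the levels of general anxiety and cancer-specific worry between women who receive risk-stratified screening and women who receive standard screening". Two instruments are named: "the STAI short form to assess general state anxiety (1992) and the Lerman cancer-worry scale (1991". The section ranks them for this purpose, reporting as a general finding that "cancer-specific worry measures are more sensitive to the effects of receiving risk information than more general measures of anxiety". It credits general anxiety measures with a different strength, a better link to diagnosed psychological disorders, and so decides to use both. On timing it states: "There is also evidence that both general anxiety and cancer-related worry peak shortly after receiving information on cancer risk". Because both are then reported to decline gradually, they are to be followed over time "to examine whether there are short-term increases as well as any longer-term effects". Section 1.1.12 likewise promises assessment of anxiety in both arms throughout the trial.

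**The schedule.** Table 1 (in the synopsis and again in Appendix 4) and the schedule of activities place the short-form STAI at baseline, V1, M12 ±6 months and M48 ±6 months. The V1 column is headed as belonging to the risk-based arm, and the heading of Section 7.4 restricts that contact: "only for women randomized in risk-based screening program". Section 7.3 plans no further investigator visit for the standard arm. Appendix 4 opens its list with "The following questionnaires will be used in this study". Neither that list, nor the table and forms that follow it, includes a cancer-worry scale.

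**The endpoint.** Secondary endpoint 2 (Section 3.2.2) covers anxiety and distress among the socio-psychological assessments, at baseline, 1 year and 4 years.

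**The concern.** The rationale sets an aim that the data collection cannot meet. Two things are missing: an instrument, and an early measurement in the control arm. An analysis plan cannot repair either one, because the data would not exist.

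Without a concurrent control, the baseline-to-V1 change in the risk-based arm mixes the effect of learning one's risk with whatever change follows enrolment and randomisation in any case. Without the worry scale, the outcome that the protocol itself regards as more responsive to risk information is not measured in either arm.

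What is at stake is the interpretation of a harm endpoint. Section 1.1.16 counts negative patient-reported impacts among the safety evaluations, and Section 8.4 uses yearly looks at these data to check that risk assessment does no psychological damage. A null STAI difference at month 12 could be read as showing that disclosure is psychologically harmless, although no randomised comparison was scheduled close to disclosure.

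**Working it through.** The protocol gives no sample size, standard deviation or margin for this endpoint, so it has no figure to reproduce. The check sets the passages side by side, followed by simple timing arithmetic.

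**1. Who is measured, when, and with what** (Table 1, schedule of activities, Section 7.4, Appendix 4)

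| Instrument | Arm | Baseline | V1 (8-12 weeks) | M12 ±6 | M48 ±6 |
|---|---|---|---|---|---|
| STAI short form | Risk-based | yes | yes | yes | yes |
| STAI short form | Standard | yes | no | yes | yes |
| Cancer-worry scale | Risk-based | no | no | no | no |
| Cancer-worry scale | Standard | no | no | no | no |

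The worry scale is also absent from the questionnaires listed for V0 in Section 7.3. Outside Section 1.1.24 it appears only as an entry in the reference list.

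**2. Distance from disclosure to the first randomised contrast**

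Risk is disclosed at V1, 8-12 weeks after V0. One week is 7/30.4375 = 0.230 months, so V1 falls at 8 × 0.230 = 1.84 to 12 × 0.230 = 2.76 months.

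- Nominal M12: 12 − 2.76 = 9.2 to 12 − 1.84 = 10.2 months after disclosure.
- Across the window (months 6 to 18): 6 − 2.76 = 3.2 to 18 − 1.84 = 16.2 months after disclosure.

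The rationale says that "both general anxiety and cancer-related worry peak shortly after receiving information on cancer risk". Between baseline and the opening of the M12 window, the standard arm, planned at 42,500 women (Section 8.1), has no scheduled STAI.

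**3. Order at V1.** Neither the schedules nor Section 7.4 says whether the V1 STAI is completed before or after the result is given. If before, it does not capture the reaction to disclosure even within the risk-based arm.

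**4. Would a month-3 contrast have enough women?** Take a two-sided 5% level and 80% power (both assumed). The detectable standardised difference is (1.960 + 0.842) × √(2/n), with n women per arm:

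- n = 42,500 (everyone): 0.02 SD.
- n = 21,250 (50% response, assumed): 0.03 SD.
- n = 2,125 (a 5% subsample, assumed): 0.09 SD.

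Numbers are not the constraint. The missing control measurement and the missing instrument are.

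**The case against.** Several points on the other side are fair.

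- **The harm is possible, not predicted.** A reader might infer that the protocol expects short-term distress. It does not. Section 1.2.3 says anxiety might occur but is not certain, and appears transient and low. Section 1.1.24 says the literature suggests many such harms are unlikely, and reports little evidence of raised distress in two earlier studies. This stands.
- **The endpoint as defined is delivered for the STAI.** A reader might infer that the anxiety endpoint is uninformative. Section 3.2.2 sets it at baseline, 1 and 4 years, and the STAI is scheduled then in both arms. The sentence promising a between-arm comparison names no time point, and the short-term aim is in a separate sentence. The risk-based arm's baseline-to-V1 change, its variation by risk category, and the small interview study three months after results all describe the early period. This stands, but none of it is a randomised comparison.
- **The effect may not have gone by month 12.** Section 1.1.24 gives no duration for the decline, and the window opens about 3 months after disclosure. One cannot say that the M12 contrast is placed where nothing remains to be seen.
- **Other distress items exist.** The satisfaction form (1 and 4 years) has one item on regret because of anxiety, and EQ-5D (baseline and 4 years) has an anxiety/depression item. Neither measures cancer worry.
- **The lists may be incomplete.** The opening list in Appendix 4 omits two questionnaires that the same appendix then schedules. Section 8.6.2 refers to a work package that is not at hand. Section 7.7 mentions month-3 questionnaires without naming an arm. But Section 7.7 refers back to the schedule of activities, which puts that contact in the risk-based column, and every schedule in the protocol omits the worry scale. This leaves an ambiguity to settle, not an answer.

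**Conclusion.** The point holds as an inconsistency between Section 1.1.24 and the protocol's own schedules. As written, cancer worry is scheduled zero times in either arm. Early anxiety is measured only in the risk-based arm, so a short-term change can be described there but not compared with randomised controls. The first randomised STAI contrast after baseline comes nominally 9-10 months after disclosure (about 3-16 months across the window). The yearly review in Section 8.4 rests on the same data.

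It would go too far to conclude that the trial cannot assess psychological harm: the between-arm STAI comparisons at M12 and M48 are sound for longer-term anxiety. The primary and key secondary analyses are not affected. The change should be made, but it concerns one secondary harm endpoint.

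The conclusion assumes that the schedules govern what is collected, that disclosure takes place at 8-12 weeks as planned, and that no document outside the protocol adds the missing measurements.

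**What to change.** Amend Table 1 (both places), the schedule of activities and Appendix 4 together:

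1. Add the cancer-worry scale named in Section 1.1.24 wherever the STAI is given, in both arms.
2. Send the 6-item STAI and the worry scale online to the standard arm at about month 3, in the same window as V1. Align Section 7.7 with this.
3. State that the risk-based arm completes both forms after risk disclosure.
4. Add to secondary endpoint 2 the between-arm difference at month 3 in anxiety and in worry, adjusted for the baseline value.

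If the sponsor does not want the extra collection, the alternative is to withdraw the short-term between-arm and cancer-worry claims from Section 1.1.24 and to describe the V1 STAI as an uncontrolled within-arm measure.

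The cost is a protocol amendment with ethics approval in five countries, language versions of one short scale, a few minutes of participant time, and some missing month-3 data in the standard arm. The existing portal can carry the forms, so no extra visit or site staff are needed. Women already past month 3 when the amendment takes effect could not contribute to the new contrast. The detectable differences above suggest that even a modest fraction of the remaining recruits would give useful precision.

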1.1.26 Long-term follow-up in MyPeBS

Although the intervention in MyPeBS will only last for 4 years, part of its consequences could last longer, especially in so-identified high risk women, who may continue both the more intense screening they have been proposed, as well as risk-reducing strategies they were advised on. It is therefore crucial we can have access to long-term stage II and higher breast cancer incidence, as well as long-term breast cancer specific mortality.

We intend to retrieve such data at 10- and 15-years from study entry.

This will allow first to identify the long-term effect of risk-based screening program as compared to standard screening, but also to refine long-term risk assessment and risk scores, in this very carefully annotated cohort.

To this end, we will not be able to retrieve data from participants nor investigators, who will not be asked any more participation after 4 years. We have therefore organised towards being able to cross our database with national health system databases and national security insurance systems databases, in each country.

1.1.27 Long-term additional research developments based on MyPeBS' database, rationale for collection of images and saliva DNA

Finally if risk-based screening is demonstrated as more efficient and more acceptable for women than standard screening, it will become crucial that risk identification can be further refined in the future.

This refinement would also dramatically serve prevention programs in the future.

It is highly likely that germline DNA can contribute to such risk identification refinement in the future, not only through the discovery of new SNPs, but also to avenues open by the potential of whole genome sequencing, and epigenetic assessments, for example.

Beside this, mammographic and other images also are of great promise for the purpose of risk identification.

For these reasons, we have organised towards storing saliva DNA of women who will consent to, for the purpose of additional research as described. We also wish to collect and store mammographic images of a maximum of participants, provided they have given their consent for this, as well. The informed consent form has been written accordingly.

1.2 Benefit-risk assessment

As demonstrated above, risk-based breast cancer screening is highly promising, given its potential ability to allow more screening efficacy in those who derive any benefit of such screening because of a higher breast cancer risk, together with decreasing harm in women who might not derive benefit from mammogram given their low personal breast cancer risk.

However, risk zero does not exist, and it is important to verify that a positive benefit-harm ratio is maintained for all participants throughout the trial.

The individual potential benefits and harms will be carefully explained to participants throughout the trial. They are explained in the informed consent, to allow women to make their own decision regarding not only participation to MyPeBS trial, but somehow also to screening in general.

Risk reduction measures will be maintained throughout the trial:

Trial-level risk reducing measures will always be applied to maximise the benefit-harm ratio for all (yearly reassessment of risk, reminders, 4-year mammogram for all, careful surveillance of the trial by the Ethics and Data Monitoring Committee, ...). Breast cancer awareness will be repeatedly stimulated for all participants throughout the trial. This is will even more pronounced for women in the low-risk group of the risk-based arm, who will have their next mammogram after 4 years.

1.2.1 *Effects and risks of mammography screening in the standard arm*

The benefits and harms/risks from standard mammographic screening have been extensively described in 1.1.2. We summarize them below:

- Mammographic screening has been associated with an average 20% reduction in breast cancer-specific mortality in average risk-women: The available evidence is derived from 11 randomized trials and their meta-analysis with 13 years of follow-up: The benefit is demonstrated for women over 50, while 2 studies demonstrated benefit for women aged 40-49, and others were negative, leading to divergent interpretation and recommendations throughout countries. Of note, the relative reduction in breast cancer specific mortality appears higher for women actually attending screening. Trials indicated no statistically significant reductions in all-cause mortality with screening. Risk for higher-stage breast cancer was reduced for age 50 years and older (RR 0.62 [95% CI, 0.46 to 0.83]; 3 trials), but not for age 39 to 49 years old (RR 0.98 [95% CI, 0.74 to 1.37]; 4 trials).
- As stated before (1.1.2), this is not without potential harms. Screening can lead to false-positive recalls, estimated to occur in more than half of the women after 10 years of annual screening; and many unnecessary biopsies: Another risk is overdiagnosis, which is currently estimated to occur in about 10% of breast cancers diagnosed through screening, although estimates range from 1% to 30%, depending on the population and estimation methods. Finally, mammographic screening is also associated with a small lifetime risk of radiation-induced cancer.

Tomosynthesis with mammography reduces recalls (16/1,000), but increases biopsies (1.3/1,000) and cancer detection (1.2/1,000): Even if concern exists regarding radiation doses administered; tomosynthesis remains therefore an option, but not a standard of mammographic screening.

